2.2.1 Subgroup of interest

No subgroups are defined in this study.

2.3 Patient disposition, demographics and other baseline characteristics

2.3.1 Patient disposition

The following summaries will be provided overall and by treatment group: % based on the total number of FAS patients:

- Number of screened patients
- Number (%) of patients who were randomized
- Number (%) of patients who were randomized but not treated.
- Number (%) of patients who were treated
- Number (%) of patients who discontinued the study treatment phase

- Primary reason for study treatment phase discontinuation
- Number (%) of patients who have discontinued the study
- Reasons for discontinuation from the study.

Patient randomization numbers whether they completed or discontinued from the study will be listed, with date of last dose and primary reason for discontinuation, including the unblinding date if applicable.

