2.2 Analysis sets

The **Screened Set (SCR)** will consist of all patients who provided informed consent

The **Full Analysis Set (FAS)** will be comprised of all randomized patients who meet both of the following criteria:

- Received at least one dose of study treatment
- Have a baseline NPS score ≥ 4 as measured by the central reader.

According to the intent to treat principle, subjects will be analyzed according to the treatment they have been assigned to at the randomization. However, if patients received study treatment without being randomized into the study they will be excluded from the FAS.

The **Safety Set (SAF)** includes all subjects who received at least one dose of study treatment. Subjects will be analyzed according to the study treatment received, where treatment received is defined as the randomized/assigned treatment if the patient took at least one dose of that treatment or if the patient received more than one treatment, then the patient would be analyzed according to the randomized treatment.

The analysis of the primary objectives will be performed on the FAS. The FAS will be used for the analysis of all other efficacy variables. The SAF will be used in the analysis of all safety variables.

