2.3.3 Analysis sets

The number of subjects included in each analysis set will be tabulated. Reasons for exclusion from the analysis sets will be tabulated for FAS. Patient exclusion from analysis sets will be listed for all patients with reason for exclusion (including protocol deviations)

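### Disposition percentages are based on the FAS, which by definition leaves out some of the randomised patients that the table counts

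*SAP*

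**What the plan says.** SAP 2.3.1 plans one disposition summary, overall and by treatment group, with percentages "based on the total number of FAS patients". The rows that carry a percentage include "Number (%) of patients who were randomized", "Number (%) of patients who were randomized but not treated" and "Number (%) of patients who were treated", together with discontinuation from the treatment phase and from the study. Screened patients appear as a count only.

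SAP 2.2 says that the FAS "will be comprised of all randomized patients who meet both of the following criteria": "Received at least one dose of study treatment" and "Have a baseline NPS score ≥ 4 as measured by the central reader". Protocol 12.1 has the same definition. SAP 5.5 repeats the exclusions as deviation rules. TRT02 (randomised, no drug given) and INCL02C (low polyp score) remove a patient from the FAS. INCL02B and EXCL19 remove a patient from every analysis set.

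Two neighbouring tables also use the FAS. SAP 2.3.2 tabulates protocol deviations for the FAS and lists them by patient. SAP 2.3.3 says "Reasons for exclusion from the analysis sets will be tabulated for FAS", and its next sentence promises a listing of exclusions for all patients, with reasons.

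SAP 2.4.1.1 refers to a randomised set, but SAP 2.2 defines only the Screened Set, the FAS and the Safety Set. SAP section 4 records no change from the protocol analyses. Neither document gives another base for the disposition percentages.

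**The concern.** A disposition percentage is meaningful when the patients in the numerator belong to the denominator. Here the denominator is a subset of the patients counted in several rows, so those rows are not proportions. One row counts exactly the patients that the first FAS criterion removes.

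Readers use this table to judge attrition and exclusion after randomisation, arm by arm. That matters in this trial because the FAS drops some randomised patients while the analysis is described as intention to treat. If the base shrinks by a different amount in each arm, equal discontinuation counts print as unequal rates.

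**Working it through.** **Inputs.** The row list and the percentage base come from SAP 2.3.1, and the FAS definition from SAP 2.2 and 5.5. The planned size of 93, with 31 per arm, comes from SAP section 3 and Protocol 12.8.1. The documents give no expected number of exclusions or discontinuations and no disposition figure to reproduce. All counts below other than 93 and 31 are assumptions for illustration.

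**Notation.** R = randomised; U = randomised but never dosed; V = randomised and dosed but outside the FAS, for example with central NPS below 4. Then FAS = R − U − V.

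**Percentages as the SAP defines them**
- Randomised: 100·R/(R − U − V). This is never below 100 and exceeds 100 once U + V ≥ 1.
- Randomised but not treated: 100·U/(R − U − V). None of the U patients is in the denominator.
- Treated: 100·(R − U)/(R − U − V). This exceeds 100 once V ≥ 1.
- Discontinued, with D counted among all randomised patients: 100·D/(R − U − V). This is the rate 100·D/R multiplied by R/(R − U − V).

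**Overall, R = 93**

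| U | V | FAS | Randomised | Not treated | Treated |
|---|---|---|---|---|---|
| 0 | 0 | 93 | 100.0% | 0.0% | 100.0% |
| 1 | 0 | 92 | 101.1% | 1.1% | 100.0% |
| 1 | 1 | 91 | 102.2% | 1.1% | 101.1% |
| 2 | 3 | 88 | 105.7% | 2.3% | 103.4% |

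With R as the base, the last line becomes 100%, 2/93 = 2.2% and 91/93 = 97.8%. The last two then add to 100%.

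**By total number outside the FAS, k = U + V, with an assumed D = 12 (12/93 = 12.9%)**

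| k | Randomised | Discontinued |
|---|---|---|
| 2 | 93/91 = 102.2% | 12/91 = 13.2% |
| 4 | 93/89 = 104.5% | 12/89 = 13.5% |
| 6 | 93/87 = 106.9% | 12/87 = 13.8% |

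**By arm, R = 31.** Suppose two patients are outside the FAS in one arm and none in another, with 4 discontinuations in each. The randomised row then reads 31/29 = 106.9% against 100%. Discontinuation reads 4/29 = 13.8% against 4/31 = 12.9%. The whole difference comes from the base.

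**Alternative reading.** Suppose the numerators were also limited to FAS members. The randomised and treated rows would then always be 100% and the untreated row always 0, so those rows would carry no information.

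**Deviation table.** A patient removed from the FAS under SAP 5.5 is not in the population of the SAP 2.3.2 table. The deviation that caused the removal is therefore missing from that table, though not from the listings.

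**The case against.** The case on the other side is mainly about consequence, and much of it stands.

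- **The excess over 100% is conditional and probably small.** If every randomised patient is in the FAS, the randomised row is exactly 100%. Protocol 8.3.1 and Appendix 7 require the central baseline reading before randomisation, so a dosed patient with central NPS below 4 would be a protocol deviation. Untreated randomised patients are foreseen, however: Protocol 8.1.1 classes them as early terminators and SAP 2.3.1 gives them a row. Once that row is non-zero, the randomised row must exceed 100%.
- **The facts stay recoverable.** Each row gives a count by arm, so a reader can recompute the rates. Patients are listed with date of last dose and reason for discontinuation. A reader might infer that attrition could not be judged from this report; the documents do not support that.
- **Exclusions do not disappear.** SAP 2.3.3 might be read as hiding the reasons for exclusion from the FAS. That goes too far: the section tabulates the size of each analysis set and lists exclusions for all patients with reasons, and its wording on the table can mean reasons for exclusion from the FAS. The gap holds for the SAP 2.3.2 table only, and there too deviations are listed by patient.
- **All randomised patients is not a complete base either.** Rule TRT01 covers patients who received drug without being randomised. They could be counted as treated yet would lie outside that base, so they need separate handling.

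None of this supplies another denominator or removes the mismatch in SAP 2.3.1.

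**Conclusion.** The rule in SAP 2.3.1 is wrong as written, and the correction is minor. The mismatch in the untreated row follows from the FAS definition alone and needs no assumption. The excess over 100% in the randomised and treated rows, and the inflated discontinuation percentages, require at least one patient outside the FAS. The inflation also assumes that discontinuations are counted among all randomised patients.

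The size is unknown in advance. In the overall illustration with 2 to 6 patients outside the FAS, the discontinuation rate moves by less than one percentage point. The effect is proportionally larger within an arm of 31, and it differs between arms if exclusions do.

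The effect is confined to descriptive tables. The primary analysis, the familywise error rate and the power do not depend on this denominator.

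**What to change.** 1. **SAP 2.2:** define a Randomised Set of all randomised patients, by assigned arm. SAP 2.4.1.1 already refers to one.
2. **SAP 2.3.1:** use that set as the base for every percentage, overall and by assigned arm. Keep screened patients as a count only. Report any patients treated without randomisation (TRT01) separately, as a count.
3. **SAP 2.3.2:** use the Randomised Set as the population for the deviation table.
4. **SAP 2.3.3:** reword so that the table gives reasons for exclusion from the FAS among all randomised patients.
5. Leave the FAS as the efficacy population.

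The cost is one set definition, short edits to three subsections and the matching table shells. No new data are needed, and the efficacy analyses do not change.

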2.3.2 Protocol Deviations

The number of subjects with protocol deviations will be tabulated by category and deviation for the FAS. Protocol deviations will be listed with date and study day of occurrence and deviation.

2.3.3 Analysis sets

The number of subjects included in each analysis set will be tabulated. Reasons for exclusion from the analysis sets will be tabulated for FAS. Patient exclusion from analysis sets will be listed for all patients with reason for exclusion (including protocol deviations)

2.3.4 Demographics and baseline characteristics

Demographics and baseline characteristics will be summarized by treatment group using the FAS set. Summaries would include age, gender, race, ethnicity, height, weight, BMI and baseline ACQ-5. Continuous variables will be summarized using descriptive statistics (number of non-missing data, mean, standard deviation, median, first and third quartiles, minimum, and maximum) and categorical variables will be summarized in terms of the number and percentage of patients in each category including a category for missing data if any for the treatment group.

No statistical analyses will be provided for baseline comparability among the treatment groups.

Derivation of BMI :

- BMI is calculated as : $BMI (kg/m^2) = \text{weight (kg)} / [\text{Height(m)} * \text{Height (m)}]$

Medical history

Medical history will be coded with the Medical Dictionary for Regulatory Activities terminology (MedDRA) using the most recent version at the time of database lock. History/conditions as well as protocol solicited events for nasal polyposis will be summarized for the FAS set by primary system organ class and preferred term. Verbatim recorded history/conditions will be listed together with the coded terms, date of diagnosis/surgery and whether the problem was ongoing at start of the study.

2.4 Treatments (study treatment, rescue medication, concomitant therapies, compliance)

2.4.1 Study treatment / compliance

Since the study has a double dummy design, each patient will be dispensed two bottles of study medication at the dispensing visits. Bottle 1 has study medication corresponding to 150 mg QAW039 or placebo and Bottle 2 has study medication corresponding to 450 mg QAW039 or placebo. Exposure and compliance will be presented on the SAF. Exposure will be presented for each treatment while compliance will be presented by treatment arm for each of the bottles separately.

The SAF will be used for the analyses of treatments. Categorical variables will be summarized as frequencies and percentages. For continuous data, mean, standard deviation, median, 25th and 75th percentiles, minimum and maximum will be presented.

2.4.1.1 Duration of exposure

Duration of exposure to a study drug will be calculated as the number of days between the first dose date and the last dose date exposed to that treatment over the specified period (expressed as: Duration of exposure (weeks) = (Date of last known dose of study drug – Date of first dose of study drug + 1)/7).

In addition, the duration of exposure will be summarized as a categorical variable classified into ≤ 4 weeks, > 4 – 8 weeks, > 8 – 12 weeks and > 12 weeks.

Dose administration data will be listed for patients in the SAF.

Patients in the randomized set who received any wrong study medications will be listed. These patients will be identified using the information recorded on the DAR page of the eCRF. If there is a record with reason = dispensing error, then the pack number will be used to identify whether or not the patient received the wrong study drug.

The number of patients with dose adjustments (interruption, or permanent discontinuation) and the corresponding reasons will be summarized for the study treatment.

2.4.1.2 Compliance

Compliance with study medication over the course of the entire study will be summarized as the percentage of days with study medication intake during the period from first intake to last intake taking into account the duration of the drug interruptions.

Percentage of days with study medication intake = $100 \times \text{number of days with non-zero study treatment intake} / (\text{Day of last Treatment} - \text{Day 1} + 1)$.

Compliance will be categorized as <80%, 80-100%, >100%, and summarized by treatment arm for each of the pills separately based on the safety set.

2.4.2 Prior, concomitant and post therapies

Concomitant medications and significant non-drug therapies prior to and after the start of the study treatment will be listed and summarized according to the Anatomical Therapeutic

Chemical (ATC) classification system in the Safety Analysis Set. More than one ATC class per medication is possible and the medication will be reported under all applicable classes.

Medications started and stopped prior to study drug and taken concomitantly will be summarized by treatment group in separate tables in the SAF. The medication will be classified into “prior” , “concomitant” based on the start/end dates.

Prior: Any medication with a start date before Day 1.

Concomitant: Any medication with end date on or after Day 1 or ongoing at the end of trial or missing end date and start date before the end of the Treatment Epoch.

Medications can be considered both prior and concomitant.

Concomitant nasal polyp related medications will be summarized

All summaries will be by treatment group on the Safety Set.

2.5 Analysis of the primary objective

2.5.1 Primary endpoint

The primary analysis of this study will be conducted according to the intention to treat principle and will be based on the FAS.

The primary population considered here are patients with nasal polyps with a Nasal Polyp Score (NPS) ≥ 4 (minimum of 2 per nostril) and a concomitant diagnosis of asthma.

The primary aim of the study is to evaluate a change in nasal polyp size with fevipiprant (150 mg or 450 mg once daily, separately) as compared to placebo. This will be evaluated by using the NPS assessed by nasal endoscopy. The total NPS is recorded as the sum of the right and left nostril scores with a range of 0 to 8 . A decrease in the NPS is considered a favorable outcome.

The primary endpoint for this study is the mean change in terms of reduction in polyp size as measured by the nasal polyp score (NPS) from baseline to week 16, for patients treated with fevipiprant (150 mg or 450 mg once daily, separately) as compared to placebo.

2.5.2 Statistical hypothesis, model, and method of analysis

The primary null hypotheses are:

- $H_{0\ 450}$: the reduction in the polyp size at 16 weeks from the baseline as measured by the NPS in fevipiprant 450 mg QD plus the SoC is less than or equal to the reduction in the polyp size as measured by the NPS in placebo plus the SoC for the population.
- $H_{0\ 150}$: the reduction in the polyp size at 16 weeks from the baseline as measured by the NPS in fevipiprant 150 mg QD plus the SoC is less than or equal to the reduction in the polyp size as measured by the NPS in placebo plus the SoC for the population.

[figure not shown]
The primary alternative hypotheses are:

- $H_{A\ 450}$: the reduction in the polyp size at 16 weeks from the baseline as measured by the NPS in fevipiprant 450 mg QD plus the SoC is greater than the reduction of the polyp size as measured by the NPS in placebo plus the SoC for the population
- $H_{A\ 150}$: the reduction in the polyp size at 16 weeks from the baseline as measured by the NPS in fevipiprant 150 mg QD plus the SoC is greater than the reduction of the polyp size as measured by the NPS in placebo plus the SoC for the population

Familywise Type I error rate control

The familywise type I error rate will be controlled at a 1-sided 2.5% level across the primary null hypothesis using graphical approach specified by Figure 2-1 (Bretz et al 2011). The Dunnett test will be used to test $H_{0\ 450}$ and $H_{0\ 150}$

Figure 2-1 Representation of Approach to Test Hypothesis

Vertices with associated weights denote the individual null hypotheses and their local significance levels (initially the alpha is split 50%:50% across the primary null hypotheses regarding the two dose levels). Directed edges between the vertices specify how the local significance levels are propagated in case of significant results.

Statistical model for primary variable

The primary efficacy endpoint is mean change in nasal polyp score from baseline to Week 16. Baseline NPS is defined as the last measurement performed on or before the date of randomization. The absolute change from baseline NPS values will be defined as the NPS at the timepoint minus the NPS at baseline.

The primary efficacy variable will be analyzed using a mixed model repeated measures (MMRM) approach (fevipiprant 450 mg plus SoC and fevipiprant 150 mg plus SoC). The model will include change from baseline to follow-up timepoints every 8 weeks through week 16 as response variables, fixed-effects factors for treatment, visit, treatment \times visit interaction, nasal

polyp score baseline value, and baseline \times visit interaction. An unstructured correlation structure will be assumed for the repeated measures within patients. Parameters will be estimated using the restricted maximum likelihood method with the Newton- Raphson algorithm. The least square mean change in nasal polyp score from baseline to week 16 alongside with 95% confidence interval and the P-value corresponding to the least square mean difference will be presented. The change in the least square mean will also be plotted by visit.

The change from baseline in NPS will be summarized by treatment arm and timepoint

2.5.3 Handling of missing values/censoring/discontinuations

Despite all attempts to ensure complete follow-up for all patients, some patients may not be followed for nasal polyp size for the whole planned study duration of 16 weeks. The primary analysis will be done using a Mixed Model Repeated Measures (MMRM) approach. Under the assumption that the missing values are missing at random (MAR), this provides asymptotically unbiased and consistent estimates of the treatment effects.

2.5.4 Supportive analyses

Sensitivity Analysis 1: A responder analysis of patients achieving a reduction of at least 1 in the Nasal Polyp score would be performed using a logistic regression, including covariates for treatment, visits and interaction between treatment and visit.

If the data suggests a logistic regression model is not the most appropriate for a responder analysis (*possible reasons may include majority of a particular response*) we will use additional analysis methods such as Cochran Mantel Haeszel test for the relative proportion of responders in each treatment arm and check whether there is a significant difference among them.

Sensitivity Analysis 2: The primary efficacy endpoint will be evaluated using the MMRM approach after imputing the Nasal Polyp Scores following surgery, only for patients who are considered as study withdrawals due to undergoing surgical procedures, by using the last observation carried forward (LOCF) technique. All other missing values will be imputed under the MAR approach within the MMRM model.

Sensitivity Analysis 3: The primary efficacy endpoint will be evaluated using the MMRM approach after imputing the Nasal Polyp Scores following surgery only for patients who are considered as study withdrawals due to undergoing surgical procedures, by using the worst observed score for that patient. All other missing values will be imputed under the MAR approach within the MMRM model.

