## Glossary of terms

Assessment	A procedure used to generate data required by the study
Cohort	A specific group of subjects fulfilling certain criteria
Control drug	Any drug (an active drug or an inactive drug, such as a placebo) which is used as a comparator to the investigational drug being tested in the trial
Dosage	Dose of the study treatment given to the subject in a time unit (e.g. 100 mg once a day, 75 mg twice a day)
Enrollment	Point/time of subject entry into the study at which informed consent must be obtained (i.e. prior to starting any of the procedures described in the protocol)
Epoch	Interval of time in the planned conduct of a study. An epoch is associated with a purpose (e.g. screening, randomization, treatment, follow-up), which applies across all arms of a study.
Investigational drug	The study drug whose properties are being tested in the study; this definition is consistent with US CFR 21 Section 312.3 and Directive 2001/20/EC and is synonymous with “investigational new drug” or “test substance”
Investigational treatment	All investigational drug(s) whose properties are being tested in the study as well as their associated treatment controls. This includes any placebos, any active controls, as well as approved drugs used outside of their indication/approved dosage or tested in a fixed combination. Investigational treatment generally does not include other treatments administered as concomitant background therapy required or allowed by the protocol when used within approved indication/dosage.
Medication number	A unique identifier on the label of each study drug package in studies that dispense study drug using an IRT system.
Non-investigational medicinal Product (NIMP)	Products which are not the object of investigation (e.g. any background therapy administered to each of the clinical trial subjects, regardless of randomization group, rescue medication, active drug run-ins etc.)
Patient	An individual with the condition of interest
Period	A minor subdivision of the study timeline; divides phases into smaller functional segments such as screening, baseline, titration, washout, etc.
Premature subject withdrawal	Point/time when the subject exits from the study prior to the planned completion of all study drug administration and assessments; at this time all study drug administration is discontinued and no further assessments are planned.

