Randomization number	A unique identifier assigned to each randomized subject, corresponding to a specific treatment arm assignment
Screen Failure	A subject who is screened but is not treated or randomized
Stage	A major subdivision of the study timeline; begins and ends with major study milestones such as enrollment, randomization, completion of treatment, etc.
Study completion	Point/time at which the subject came in for a final evaluation visit or when study drug was discontinued whichever is later.
Study drug/treatment	Any drug (or combination of drugs) administered to the subject as part of the required study procedures; includes investigational drug, active drug run-ins or background therapy.
Study treatment	Any drug administered to the study participants as part of the required study procedures; includes investigational drug (s), control(s) or non-investigational medicinal product(s)

Study treatment discontinuation	When the subject permanently stops taking study treatment prior to the defined study treatment completion date
Subject	An individual who has consented to participate in this study. The term Subject may be used to describe either a healthy volunteer or a patient.
Subject number	A unique number assigned to each subject upon signing the informed consent. This number is the definitive, unique identifier for the subject and should be used to identify the subject throughout the study for all data collected, sample labels, etc.
Variable	A measured value or assessed response that is determined in specific assessments and used in data analysis to evaluate the drug being tested in the study
Withdrawal of consent (WoC)	Withdrawal of consent from the study is defined as when a subject does not want to participate in the study any longer, and does not want any further visits or assessments, and does not want any further study related contact, and does not allow analysis of already obtained biologic material

## Amendment 3

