- If a patient undergoes nasal surgery, including but not limited to the following: treatment of nasal polyposis, septal deviation correction, turbinectomy, para-nasal sinus drainage, nasal plastic surgery, hypophysis tumor nasal approach.
- If a patient develops a medical condition, that requires consistent use of prohibited treatment as per [Section 6.2.2](#) or if patient exhibits a behavior of non-compliance regarding prohibited medication.

If discontinuation of study treatment occurs, the Investigator should make a reasonable effort to understand the primary reason for the subject's premature discontinuation of study treatment and record this information.

[figure not shown]
Subjects who discontinue study treatment or who decide they do not wish to participate in the study further should NOT be considered withdrawn from the study UNLESS they withdraw their consent (see withdraw of informed consent section.). **Where possible, they should return for the assessments indicated** in the Assessment schedule ( [Table 8-1](#) ).

After study treatment discontinuation, at a minimum, in abbreviated visits, the following data should to be collected at clinic visits or via telephone visits:

- new/concomitant treatments including OCS use
- adverse events/Serious Adverse Events

If they fail to return for these assessments for unknown reasons, every effort (e.g. telephone, e-mail or letter) should be made to contact the subject/pre-designated contact as specified in the lost to follow-up section. This contact should preferably be done according to the study visit schedule.

If the patient cannot or is unwilling to attend any visit(s), the site staff should maintain regular telephone contact with the patient, or with a person pre-designated by the patient. This telephone contact should preferably be done according to the study visit schedule. The information already collected during the study including your samples will still be used according to applicable laws

The Investigator must also contact the IRT to register the patient's discontinuation from study treatment.

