## **12 Data analysis and statistical methods**

The primary efficacy and safety analyses will be conducted at the time the trial ends. All data captured in the study up to the end of study will be analyzed and reported.

Any data analysis carried out independently by the Investigator should be submitted to Novartis before publication or presentation.

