2.1.1 Data included in the analysis

The analysis cut off date is defined as the date of last patient last visit during the 2 week follow-up period post the 16 weeks treatment period. The entire data collected up to the cut off date would be used under the scope of the analysis defined in the subsequent sections. All data with an assessment date or even start date (e.g. vital sign assessment date or start date of an adverse event) prior to or on the cut off date will be included in the analysis. Any data collected beyond the cut-off date will not be included in the analysis and will not be used for any derivations.

All events with start date before or on the cut-off date and end date after the cut-off date will be reported as 'continuing at the cut-off date'. The same rule will be applied to events starting before or on the cut-off date and not having documented end date. This approach applies, in particular, to adverse event and concomitant medication reports. For these events, the end date will not be imputed and therefore will not appear in the listings

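### The two surgery sensitivity analyses cover only patients counted as study withdrawals, a status the protocol does not give a patient merely for having nasal surgery

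*SAP*

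**What the plan says.** Protocol 12.4.4 and SAP 2.5.4 describe two repeats of the primary MMRM in which scores after surgery are imputed. Sensitivity Analysis 2 uses last observation carried forward (LOCF), and Sensitivity Analysis 3 uses the patient's worst observed score. Both apply "only for patients who are considered as study withdrawals due to undergoing surgical procedures". All remaining missing scores are left to the model under missing at random.

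Protocol 9.1.1 deals with the same event differently. Its list of circumstances in which study treatment must stop includes: "If a patient undergoes nasal surgery, including but not limited to the following: treatment of nasal polyposis". The section then says that subjects who discontinue study treatment "should NOT be considered withdrawn from the study UNLESS they withdraw their consent", and adds: "Where possible, they should return for the assessments indicated". The minimum data set after stopping is concomitant treatments and adverse events, so endoscopy is requested but not guaranteed.

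The protocol glossary keeps the two states apart. Study treatment discontinuation is defined as: "When the subject permanently stops taking study treatment prior to the defined study treatment completion date". Premature subject withdrawal is leaving the study, and "at this time all study drug administration is discontinued and no further assessments are planned".

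On which data are used, protocol section 12 says: "All data captured in the study up to the end of study will be analyzed and reported". SAP 2.1.1 says: "The entire data collected up to the cut off date would be used". Neither document has a rule for an NPS measured after surgery.

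**The concern.** Polyp surgery removes what the NPS measures. Sensitivity Analyses 2 and 3 are there to show how far surgery influences the primary result. They can do so only if they reach the patients whose scores surgery has changed.

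Under 9.1.1, surgery on its own makes nobody a study withdrawal. Taken at face value, the subset is operated patients who also withdraw consent, and protocol 9.1.2 allows no further assessments for them. The patient who is operated on, stays and is scored again falls outside it. For that patient both analyses would simply repeat the primary analysis. Two programmers working from the present text could also produce different versions of the same analysis.

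**Working it through.** **1. Following an operated patient through the documents.**

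- Surgery occurs, so study treatment stops (protocol 9.1.1).
- Study status: not withdrawn unless consent is withdrawn (protocol 9.1.1).
- Later visits: asked to return where possible. NPS is scored at weeks 8 and 16 (protocol 8.3.1).
- Primary analysis: a measured score enters by default. SAP 2.5.3 covers missing values only, and the SAP 5.4.1 code selects on visit, not on surgery.
- Sensitivity Analyses 2 and 3: the patient is not a study withdrawal, so the score is left as measured.

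A measured score can also come from a discontinuation visit. Protocol Table 8-1 includes endoscopy in the column for end of treatment or treatment discontinuation. SAP 2.1.3.10 permits remapping such a visit to the nearest scheduled visit that did not occur. With visits on days 28, 56, 84 and 112, the midpoints are days 42, 70 and 98. Days 43 to 69 (27 days) therefore map to week 8, and days 99 to 112 (14 days) to week 16. Only the second window feeds the week-16 contrast directly.

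**2. The looser reading.** Suppose that withdrawal was meant to cover everyone who stops treatment because of surgery. Two questions stay open:

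- Is a measured post-surgery score overwritten, or only a missing one filled? The object of imputation is the scores following surgery, which suggests overwriting. The phrase about all other missing values suggests that those scores were expected to be missing.
- Must the carried-forward or worst score predate surgery? If the last observation is a post-surgery endoscopy, LOCF carries the surgical result forward.

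**3. Plan figure used for scale.** From SAP section 3: difference 1.5, SD 1.8, one-sided alpha 0.0125, power 80%, dropout 10%. The normal approximation gives n = 2 × (2.241 + 0.842)² × 1.8² / 1.5² = 27.4, so 28 per arm. Then 28 × 1.1 = 30.8, so 31 per arm and 93 in total, as stated. I take 28 evaluable per arm.

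**4. Illustration.** These inputs are assumptions, not document figures: one operated and re-scored patient in an arm, a change from baseline of −c after surgery with c from 3 to 5 (at most 4 if baseline is 4), and a pre-surgery change of 0. Simple week-16 means stand in for the MMRM.

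- Shift in the arm mean is c/28: 3/28 = 0.107, 4/28 = 0.143, 5/28 = 0.179.
- Standard error of the difference is 1.8 × √(2/28) = 0.481. The shift is 0.107/0.481 = 0.22 to 0.179/0.481 = 0.37 standard errors.

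For a true difference of 1.5 (placebo mean change 0, active −1.5):

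| Operated and re-scored | Primary, and Analysis 2 read literally | Analysis 2 defined by surgery |
|---|---|---|
| One on placebo | 1.5 − c/28 = 1.39 to 1.32 | 1.50 |
| One on an active arm | (27 × 1.5 + c)/28 = 1.55 to 1.63 | 40.5/28 = 1.45 |
| One on each | 40.5/28 = 1.45 for any c | 1.45 |

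The literal version removes none of the shift, and the surgery-based version removes all of it. The direction depends on the arm, and balanced surgery has little effect.

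**The case against.** The strongest answer is that the literal reading is not what the authors meant. If study withdrawal requires withdrawn consent, a withdrawal due to surgery is nearly an empty category, and nobody writes two analyses for almost no patients. The Amendment 2 summary calls the surgery rule a withdrawal criterion and adds the sensitivity analyses in the same amendment. Protocol 9.1.1 itself uses withdrawal loosely for excess corticosteroid use, in a list about stopping treatment, and 6.6.2 does so for code breaks. Nor does 9.1.1 repeat the not-withdrawn rule for surgery specifically. It applies because surgery is on the list.

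Much of this stands. It makes the wider reading plausible and the issue one of ambiguity. It does not settle whether measured scores are replaced or which values replace them.

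It is also fair to say that the size is assumed throughout. Post-discontinuation endoscopy is only requested, remapping is only permitted, and no operated patient may ever be re-scored. A reader might infer a serious loss of power by supposing several re-scored operated patients on placebo and none on active treatment. Nothing in the documents supports that pattern.

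**Conclusion.** The wording of Sensitivity Analyses 2 and 3 conflicts with protocol 9.1.1. Read literally, they miss operated patients who stay and are re-scored. Read loosely, their imputation rule is incomplete. One such patient would shift an arm mean by 0.11 to 0.18, or 0.2 to 0.4 standard errors of the difference. This rests on 28 evaluable per arm, SD 1.8, an assumed fall of 3 to 5 points and no pre-surgery change. How many patients are affected is unknown and may be none.

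Two stronger conclusions are tempting, and the documents support neither. A reader might infer that the primary MMRM is wrong because it takes in post-surgery scores. Using observed scores fits the intention-to-treat and all-data wording and is a permissible strategy. A reader might also infer that the responder analysis (Sensitivity Analysis 1) is in error because a surgical fall of at least 1 point counts as a response. That too depends on which estimand the sponsor wants.

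Severity is minor. The affected analyses are supportive and carry no alpha, and the primary test and sample size are unchanged.

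**What to change.** Before unblinding, amend SAP 2.5.4 as follows:

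- **Subset.** All FAS patients with nasal surgery that affects the polyp score, after first dose and before the week-16 endoscopy, whatever their withdrawal status. List the qualifying procedures in advance, because the 9.1.1 list also covers operations such as nasal plastic surgery and a nasal approach to a hypophysis tumor.
- **Replacement.** Replace every post-surgery NPS, measured or missing, including one from a remapped discontinuation visit. Use pre-surgery values only: the last in Analysis 2 and the worst in Analysis 3.
- **Consistency.** Reconcile this wording with protocol 9.1.1 and 12.4.4. If the SAP then departs from the protocol, record it in SAP section 4, which currently lists no changes. The amendment concerns only which patients are analysed in this way, not who stops treatment or leaves the study.

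The cost is a few sentences, a short procedure list and a derived surgery-date flag. Protocol 6.2.1 already requires procedures after enrolment to be recorded on the CRF. The downside is slightly more analysis work. Any change to the protocol text itself needs a written amendment under protocol 14.1.
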